	17.	Planned dental/oral surgery or modification (bridge-work, implants) within four weeks prior to the injection and to a minimum of four weeks post injection
	18.	Any medical condition prohibiting the inclusion for repeat-treatment according to the judgement of the treating investigator
	19.	Beard longer than three-day beard, or excessive facial hair that could interfere in evaluation of treatment as judged by the investigator

20. Previous enrollment in initial treatment phase of this clinical investigation and early termination, or significant incompliance with the protocol requirements
21. Current or previous treatment with another investigational drug and/or medical device or participation in another clinical study
22. Midface volume deficit due to a trauma, or abnormalities in facial adipose tissue distribution such as those associated with HIV related lipodystrophy
23. Subjects who experienced weight change for a minimum of 10% since study start or subjects who have the intention to change eating habits that result in a weight gain or loss >10% during the entire investigation
24. Subjects with active COVID-19 infection and subjects with symptoms consistent with COVID-19 infection including any other respiratory symptoms/illnesses within the past 14 days unless tested negative prior to Visit RT1

INVESTIGATIONAL D	EVICE(S), DOSE AND MODE OF ADMINISTRATION
Test device	saypha® VOLUME Lidocaine: Crosslinked hyaluronic acid (HA) 23 mg/mL + 0.3% lidocaine hydrochloride.
Comparator device	: Crosslinked HA 20 mg/mL + 0.3% lidocaine hydrochloride
Dose and mode of administration	The respective device will be administered by subcutaneous and/or supraperiosteal injection. The injection technique used will be selected by the treating investigator.
	For injection, either a needle (27G ½") or cannula (25G 1½") may be used in the discretion of the treating investigator. A minimum of approximately 100 subjects randomized to the test device will be treated with either needle or cannula.
	The volume administered is at the discretion of the treating investigator and depends on the severity of the midface volume deficit to be corrected.
	However, the maximum volume (left and right side of the midface together) must not exceed 10 mL in total per treatment phase (initial and repeat- treatment, respectively, including touch-up treatments) or 20 mL per 60 kg (130 lbs) body mass per year.

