# 6.1.2 Randomization

The randomization will be performed at the Baseline visit (Visit 2), after final confirmation of subject's eligibility. Treatment assignment will be pre-planned according to a computer-generated randomization schedule in a 2:1 ratio (test device : comparator device). The schedule will contain the following treatment assignments, which will be randomly allocated to sequential randomization scheme:

- Test device: saypha® VOLUME Lidocaine
- Comparator device:

The randomization information will assign the subject to one of the treatment groups. In addition, a minimum of 100 subjects randomized to the test device will be treated with either needle or cannula.

Only unblinded site staff performs the randomization via a randomization function of the eCRF.

Neither the blinded evaluator at the site nor the central independent photographic reviewer will have access to the randomization system (see section 6.1.3 for details). The randomization number will be documented in the eCRF.

The exact procedure for obtaining a randomization number/treatment assignment for a subject will be provided to each investigational site before the study is initiated by training and will be described in a separate manual or other appropriate document.

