The rater blinding regarding treatment group in initial treatment will remain in effect until study data base lock. The blinded evaluator at the site will be trained on the MVDSS and NLF-SRS prior to start of the investigation during the investigator meeting, a live WebEx with a sponsor medical consultant, or through review of a recording of the WebEx. Open questions by on-site located raters will be answered during the pre-study visits; further training on the scale will be also performed during site pre-study visits, if needed. The independent blinded photographic reviewers will be trained on the MVDSS prior to their assessments of the photographs.

In addition, the improvement of midface volume deficit will also be evaluated centrally by using computerized volume change measurement based on the 3D photographic images. The quantified data of the volume change measurement provide additional evidence confirming the effectiveness of the test device for the indication to be treated (see section 6.4.12).

The time point for definition of the primary endpoint (Week 24 after last injection of the initial treatment phase) was selected based on clinical experience with other HA fillers and will be corroborated by earlier and later observations (see Table 1 and Table 3 for details). Difference of one grade on this scale is considered to be clinically meaningful since it can be visually recognized by various observers as demonstrated during validation of the scale.

The clinical relevance of the investigation will be also supported by several (other) secondary effectiveness endpoints (see section 5.3), related to global aesthetic improvement (by using the modified GAIS) [35] and subject's satisfaction with outcome (overall and the cheeks by using FACE-QTM scales).[36, 37]

Information on occurrence of pain will be primarily obtained by collection of AEs, with additional insight into pain intensity being obtained directly after the injection using a semi-quantitative 11-point Numeric Pain Rating Scale (NRPS).[38].

Touch-up treatments are allowed in the investigation, and the treating investigator will determine the appropriate injection volume and injection technique and equipment (i.e., needle/cannula) based on his/her clinical experience (see sections 6.2). A minimum of 100 subjects randomized to the test device will be treated with either needle or cannula. Use of either needle or cannula is based on the treating investigator's medical decision.

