		• The injection technique for regard to the angle and orientation of the bevel, the depth (subcutaneous and/or submuscular/ supraperiosteal) of injection, and the quantity administered may vary depending on the area being treated. Injection of the filler too superficially (intradermally), or in large volumes over a small area, may result in visible and persistent lumps and/or discoloration.	
Injection equipment	Either needle or cannula will be used (see below) in the discretion of the treating investigator. A minimum of 100 subjects randomized to the test device will be treated with either needle or cannula.		
	• 27G ½" needle (provided with the syringe)	• 27G ½" needle (provided with the syringe)	

provided separately)

Table 15. Description of injection technique and injection equipment used in the investigation

25G 1 1/2" cannula

provided separately)

25G 1/2" cannula

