## 6.3 Subjects

## 6.3.1 Number of subjects and duration of the clinical investigation

Up to 486 subjects are planned to be randomized in a 2:1 ratio (test device: 324, comparator device: 162) and treated. Approximately 516 subjects will need to be screened to reach 486 subjects randomized (accounting for a screening failure rate of approx. 6%) and to ensure that 437 subjects will be evaluable for the primary endpoint. Approximately 300 subjects are estimated to qualify for repeat treatment.

Inclusion of subjects is planned to be as equally distributed as possible between the sites. The clinical investigation is planned to be conducted at approximately 16 study sites with enrolment target of approximately 20 to 30 subjects per site. The maximum expected number of subjects to be enrolled per each site will be 45 but may be higher if agreed with the Sponsor.

Each subject will take part in the investigation for up to 92 weeks.

The total anticipated duration of the investigation, from the first-subject-first visit to the last-subject-lastvisit, is around 114 weeks, based on expected recruitment period of about 22 weeks.

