## 6.4.10 Injection volume, injection technique and injection equipment

The following information will be documented in the subject's source record and the in eCRF:

- Injection volume (see section 6.2.3 for details)
  - the volume injected will be calculated by the investigator based on the number of syringes used and the estimated amount of the gel remaining in each of the syringes used)
  - o the injection volume will be documented separately
    - for right and left side of the midface
    - for each anatomical area of the midface (see section 6.2.2 for details)
    - per each treatment (i.e., for baseline- and repeat treatment and each touch-up treatment (if applicable)
- Kit numbers of kits used (see section 6.2.1 for details)
- Injection technique (see section 6.2.2 for details)
- Injection equipment used (i.e., needle or cannula (see 6.2.2 for details). Note: A minimum of 100 subjects randomized to the test device will be treated with either needle or cannula. Use of either needle or cannula is based on the treating investigator's medical decision. Details how to monitor enrollment levels via the eCRF system will be described in the project management plan.
- Exact start time and end time of injection

For detailed instructions on administration of the devices refer to section 6.2.2.

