#### 7.3.4 Demographics and baseline characteristics

Summary statistics for demographic and baseline characteristics, including age, gender, race/ ethnicity, and other relevant study entry criteria will be prepared for the SAF. In addition, demographic and baseline characteristics including age, gender, race/ ethnicity as well as injection equipment will be presented by study site.

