Change	CIP Sections affected	Rationale
		a visual depiction (see Figure 3) of the areas of midface treatment were added.
		This was added for patient safety and to ensure investigators are provided with clear and standardized administration instructions for the subject device and comparator.
Administration of test device was specified: Instructions given for the administration of apply now for saypha® VOLUME Lidocaine, too.	Section 6.2.2 (Table 16)	To provide same level of instruction given to treating investigators to ensure patient safety and comparable results between the 2 devices.
Applied volume of the devices per side and documentation was specified	Synopsis Section 6.2.3 Section 6.4.10	Per FDA comment: FDA raised a safety concern in the event of exaggerated asymmetric injection. Therefore, a maximum volume of device per side of the midface was defined to ensure an appropriate volume is injected per treatment area for the safety of study participants.
		As the CIP allows subjects with slight asymmetries to be enrolled (per InC#2), the expected outcome of an optimal aesthetic result will potentially require moderate differences in treatment volumes by side. This was considered when the maximum volume of 6.0 mL for one side (and 4.0 mL for the second one) was introduced.
Kit numbers of kits used will be documented in the eCRF.	Section 6.4.10	To have complete documentation of injection-related data available.
No stratification between needle and cannula (1:1) will be performed. Instead, it will be ensured via monitoring of data management overview to get a minimum of 100 subjects randomized to the test device treated with either needle or cannula.	Synopsis Section 6.1.2 Section 6.2.2 Section 6.3.1 Section 6.4.10	In general, in this study the use of needle or cannula is based on the treating investigator's medical decision. Originally it was planned to stratify in a 1:1 ratio (needle versus cannula). The approach was changed to have a setting which is more similar to real-life situation but ensures a minimum of 100 subjects treated with test device via needle or cannula, each, to collect adequate safety data.

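### Does the quota of 100 test-device subjects by needle or cannula leave the minimum for each equipment type unsecured?

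*Protocol*

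**What the plan says.** The quota appears in five places. Section 6.1.2 has "a minimum of 100 subjects randomized to the test device will be treated with either needle or cannula". Section 6.1.4 has "A minimum of 100 subjects randomized to the test device will be treated with either needle or cannula", and section 6.2.2 (Table 15) and section 6.4.10 repeat it. The synopsis softens the number: "A minimum of approximately 100 subjects randomized to the test device will be treated with either needle or cannula".

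The choice of equipment is clinical, not randomised. Table 15 states: "Either needle or cannula will be used (see below) in the discretion of the treating investigator". The planned arm sizes in section 6.3.1 are "test device: 324, comparator device: 162". Section 6.4.10 adds, in its note on equipment: "Details how to monitor enrollment levels via the eCRF system will be described in the project management plan".

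The word that would make the quota bite occurs only in section 19.1. There the sponsor explains why 1:1 stratification by equipment was dropped, and gives as the aim "a minimum of 100 subjects treated with test device via needle or cannula, each, to collect adequate safety data".

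On reporting, section 7.3.4 says that "demographic and baseline characteristics including age, gender, race/ ethnicity as well as injection equipment will be presented by study site". Section 7.3.7 summarises equipment at each injection time point by treatment group. Section 7.3.10 lists needle versus cannula among the descriptive subgroups, with an exploratory interaction model and the detail left to the SAP.

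**The concern.** A quota should be capable of being missed. If the only two options are needle and cannula, and the rule asks for 100 subjects treated with one or the other, every treated test-device subject counts towards it. An arm treated entirely by needle would comply. The protocol would then secure no cannula experience with the test device, although the sponsor gave up stratification on the understanding that both types would be represented.

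At stake are the safety summaries and the effectiveness subgroup by equipment. A thin group could also go unremarked, because under the literal wording it would not be a departure from the plan.

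A related worry is that an unblinded investigator picks the equipment, possibly after allocation. Section 7.3.10 nevertheless lists it beside gender, age and race as if it were an ordinary baseline factor.

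**Working it through.** **Inputs.** 437 evaluable subjects, 10% excluded from the per-protocol set and 2:1 allocation (section 7.1); arm sizes of 324 and 162 (section 6.3.1); quota of 100 (section 6.1.2); two permitted equipment types (Table 15).

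**Reproducing the arm size.** 437 / (1 − 0.10) = 485.6, rounded up to 486. Then 486 × 2/3 = 324 and 486 × 1/3 = 162, as stated.

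**Three readings of the quota.** Let c be the number of test-device subjects treated by cannula and 324 − c the number treated by needle, counting each subject once. Then c runs from 0 to 324, which gives 325 splits.

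| Reading | Condition | Splits that comply |
|---|---|---|
| Both types counted together | c + (324 − c) ≥ 100 | 325 of 325 |
| At least one type reaches 100 | max(c, 324 − c) ≥ 100; the maximum is never below 162 | 325 of 325 |
| Each type reaches 100 | 100 ≤ c ≤ 224 | 125 of 325 |

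The first two readings are empty. They stay empty with the 291 evaluable test-device subjects, where the larger group is at least 146. They also stay empty if a subject may be counted under both types, because every treated subject still belongs to at least one. The third reading can fail, and it is feasible because 100 + 100 = 200 ≤ 324.

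**What the counts do not show.** The 200 splits that satisfy the literal text but not the third reading are possibilities, not probabilities: 324/0 weighs as much as 162/162. If investigators chose independently with a common cannula share, the chance that both types reach 100 would be about 1% at a share of 25%, 39% at 30%, 81% at 33% and over 99.9% at 40%. The document gives no share, so none of these can be singled out.

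**What 100 per type buys.** With no events among n subjects, the one-sided 95% upper bound on the event rate is 1 − 0.05^(1/n): 2.95% at n = 100, 5.82% at 50 and 11.29% at 25. This shows why a floor was wanted. It does not show that the floor was missed.

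**Which reading is meant.** In the Amendment 1 table, the column describing the change uses the same loose phrase as the current text, and the rationale beside it explains that phrase as 100 of each. This is not a clash between superseded and current text. The sponsor is glossing its own wording, which still stands.

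**The case for a change.** The strongest case for a change is that this is a design commitment made five times, and none of the five contains the word that gives it force. It is not a matter for the SAP. The protocol passes monitoring to a project management plan without handing over a threshold for each type.

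Numbers by type also matter here. Sections 3.2.1 and 3.3 say there are no known data on the test device in bilateral midface augmentation. In the comparator's cannula study (Table 12), specific diary reactions were less frequent with cannula, for example 66.7% against 83.3%. Needles come in the test-device box and cannulas are supplied separately, so balance cannot be taken for granted. Adding one word in five places would cost little.

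Part of this stands. The wording is loose, and the synopsis differs trivially from the body on whether 100 is approximate. The protocol also does not say how to count a subject treated by needle at baseline and by cannula at touch-up.

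The rest does not carry a change. That the protocol states no threshold for the project management plan does not show that the plan lacks one. A reader who prefers an empty rule must do so against the sponsor's printed explanation. Section 19.5 reports in the past tense that all subjects were recruited at US sites, so rewording would alter nobody's treatment.

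The subgroup point is weaker still. Section 6.5.2 is a task list that puts randomisation before injection but does not say when the equipment is chosen. The protocol already calls the choice a medical decision and the interaction model exploratory. A caution about reading that interaction as effect modification belongs in the SAP or the report.

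**Conclusion.** The observation about the wording is right, but it calls for no change to the plan. The quota is badly phrased, its intended meaning is documented in the same protocol version, and that meaning is achievable within the planned arm. Nothing confirmatory rests on it: the non-inferiority test, the 437 evaluable subjects and the one-sided 0.025 level are the same under any split. The equipment counts that would reveal a shortfall are already due to be tabulated, so any reader can set them against 100 per type.

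This rests on three assumptions: that the Amendment 1 rationale states the sponsor's intent, that recruitment is complete as section 19.5 suggests, and that the planned 324 is close to the number treated. The actual needle and cannula counts are unknown. If one group proves small, the imprecision will show in the safety tables, and rewording the quota now would not remedy it.

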# 6.1.3 Blinding

The blinded evaluator at the site, who will perform live assessments of treatment effectiveness, as well as the central independent blinded photographic reviewer will be blinded to the treatment administered.

Subjects will also be blinded to the treatments they received until finalization of Visit 9 (SV1). Measurements to keep the blinding are described below.

# Subjects

- Subjects will be blinded to the treatment administered
  - Subjects will be blind-folded during treatment. Subjects might be unblinded via label or design of the syringe/backstop of both devices that are different in appearance. Before removing the blind-folds, the respective device (incl. all needles/cannulas used, the surrounding boxes/blisters, etc.) must be removed from the treating room or covered (e.g., with a

nontransparent box) before the sleep mask is removed). The way of blinding (e.g., goggles, masks, other) has to be documented in the subject's source record and in the eCRF.

- Also, the sites must ensure, that before, during and after the treatment there can be no specific information found in the clinical and especially the treating room (e.g., logos on the device or on the outer boxes; the subject must have no view on the computer screen during randomization process)
- The treating investigator and other site staff must not disclose the device injected to the subject

#### Blinded evaluator at the site

The blinded evaluator at the site will be independent of the study conduct and blinded against the randomization code of each subject until data base lock.C The following measures will be taken to ensure the blinded evaluator at the site throughout the clinical investigation:

- Each site has to install two types of study personnel:
  - Unblinded site staff (i.e., treating investigator, other site staff)
  - Blinded evaluator at the site.

Of note, unblinded site staff as well as CRO staff (including Clinical Research Associates (CRAs)), data managers, medical monitor and biostatistician) and sponsor will be unblinded to the treatment group assignment.

- The treating investigator, all other unblinded site and CRO / sponsor staff must not disclose the blinded evaluator at the site the identity of the treatment group the subjects belong to. Especially the treating investigator must ensure that the blinded evaluator at the site is not inadvertently unblinded when evaluating the subjects.
- The blinded evaluator at the site will not be present during treating investigator's evaluation of the subject or vice versa.
- The treating investigator and the blinded evaluator at the site will not discuss any details or guesses about the treatment assignment, potential touch-up or repeat-treatment, or results of assessments in individual subjects during the course of the investigation and until the final database lock. The same applies to any discussions between blinded evaluators at the site.
- The treating investigator will explain to each subject that they should not discuss, any side-effects or complaints, nor personal views on treatment success with the blinded evaluator at the site, in order to assure scientific rigor and unbiased results of the trial.
- Results of ratings will be documented on Rating Sheets by the blinded evaluator at the site (see section 6.4.12 for details).
- The blinded evaluator at the site will not have access to the subject's source records during the course of the investigation and until the final database lock. If this will not be technically feasible, e.g., in case of electronic source records, the blinded evaluator will commit to abstain from accessing these records and will maintain the list of prohibited medical files to avoid accidental access
- The blinded evaluator at the site will not have access to the eCRF to keep the blinding towards the treatment assignment of the subject. Results of the ratings will be transferred into the eCRF by an

<sup>C Note: The **blinded evaluator at the site** is *not* blinded for treatment allocation during the repeat-treatment phase. However, he/she will be blinded for the treatment a subject received during the initial treatment phase until final database lock.
unblinded team member. However, the blinded evaluator at the site will have an emergency access to the eCRF/IWRS for emergency unblinding (also see below).

- The blinded evaluator at the site will not have access to the data of the interim analysis or the interim clinical investigation report (iCIR).
- The site staff will be trained by the CRA on the required procedures to maintain the blinding of the blinded evaluator at the site.

In the event that the treatment group allocation for a subject becomes known to blinded evaluator at the site, the sponsor must be notified immediately (i.e., within 24 hours).

Unblinding a subject's treatment group to the blinded evaluator at the site must be recorded in the subject's source record, in the eCRF indicating the date and will be considered a protocol deviation. The evaluability of such subjects will be discussed at the data review meeting (DRM).

